3.3.3 Recruitment

Interested families will be invited to meet a researcher for further information if their child has a diagnosed ASD and behavioural problems in a mainstream school. We will recruit 50 children attending mainstream schools, with autism spectrum disorders (Autism, Asperger syndrome and Atypical autism), using ICD-10 research diagnostic criteria [RDC] (46), supported by ADI-R (47) and/or ADOS (48). Other developmental disorders will not be included.

Schools will be approached to take part in the study through an existing network of clinical and educational practitioners and researchers. Co-applicant [name] has previously facilitated many research studies across the full range of schools as part of his role within the Local Authority. There are 72 primary schools in the York Local Authority and 10 secondary schools. Two of these secondary schools are designated as ASD supportive schools, although all the other schools have some young people with ASD within them. We have already had preliminary discussions with a number of secondary and primary schools that are supportive of this bid and we are confident that we can recruit 30 children within primary schools and 20 young people within secondary schools without difficulty. We anticipate that this will be in 4 secondary schools and 10 primary schools, although we will test the feasibility of this and be adaptable to recruit more or less by rolling out school involvement and leaving enough time in the study for flexibility. We will stratify school randomization to take into account numbers of ASD children, levels of ASD support, socio economic indices and Ofsted value added scores. We will ask the local multi agency autism strategy group to compare the two groups of schools generated for equivalence. Any concerns will be fed back to the steering group and the matching process will be considered as part of the feasibility work.

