3.3.4 Randomization

We will adopt a cluster randomization approach. This is to minimize the likelihood of participants in the different intervention groups being affected by changes in teacher or school behaviour. It also recognizes that social story expertise within a school is likely to be enhanced by sharing of skills and networking of ideas, and this design therefore more accurately reflects what would happen if social stories were used within a school in practice. We will use the qualitative interviewing within the feasibility design to explore this further, as described below.

To reduce detection bias we will first recruit the mainstream schools to be involved in the study. Then subsequently we will consent children and their families within these selected schools for involvement in the study. Only then will we randomize the schools into schools where the intervention takes place and those where it does not but where we are monitoring outcomes in the same way as in the intervention school. Participants will be randomised at whole school level, thus all children with ASD within any given school will be randomised to the same arm of the trial. This will minimize contamination as the likelihood of participants in the different intervention groups being affected by changes in teacher or school behaviour will be reduced. In order to limit detection bias, participants will be receive the Social Story intervention. The control school children will receive an equivalent amount of time reading a story of similar length and linguistic complexity a range of which will be chosen by the expert panel as an attention control. In both schools children will receive all other treatment or support as usual and we will monitor carefully what this is.

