3.3.11 Blinding

Blinding of the participants will not be feasible, nor is blinding of all members of the study team who are actively involved in the administration of the study. However, members of the study team responsible for the statistical analysis will be kept blind to group allocation.

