6.7 Trial Steering Committee (TSC)

A TSC will be set up and will include an independent chair and at least two other independent members, along with the lead investigator and the other study collaborators.

ASSSIST Trial Protocol Version 4.1 17/06/11

Two service users will join the steering group for collaboration on monitoring study progress. They will also be consulted on methods of dissemination of study findings for service users. They will meet at least annually (See Appendix 2 for details).

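### School balance is to be judged by a local group after the draw, when it can no longer be improved safely; balance limits should be set first and one acceptable split drawn at random

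*Protocol*

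**What the plan says.** Section 3.3.3 sets the number of clusters and the method of balancing them: "We anticipate that this will be in 4 secondary schools and 10 primary schools", and "We will stratify school randomization to take into account numbers of ASD children, levels of ASD support, socio economic indices and Ofsted value added scores". The number of schools may rise or fall, because the section allows involvement to be rolled out flexibly.

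The same section then adds a review of the result: "We will ask the local multi agency autism strategy group to compare the two groups of schools generated for equivalence". On what follows from that review it says only: "Any concerns will be fed back to the steering group and the matching process will be considered as part of the feasibility work".

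Section 3.3.4 gives the order of events. Schools are recruited, families consent, and then: "Only then will we randomize the schools into schools where the intervention takes place and those where it does not". Section 3.3.11 limits blinding to the analysts: "members of the study team responsible for the statistical analysis will be kept blind to group allocation". Section 6.7 describes the steering committee: "A TSC will be set up and will include an independent chair and at least two other independent members, along with the lead investigator", together with the other collaborators and two service users.

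**The concern.** With so few clusters, chance imbalance between arms is a real problem, and the authors are right to want a safeguard. The safeguard comes at the wrong point. Before the draw, local knowledge of the schools can shape which allocations are allowed, and chance still decides among them. After the draw, the same knowledge can only describe the imbalance or prompt a change to the allocation. A description leaves balance as it is. A change made on opinion means that the arms are no longer formed by chance alone.

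This matters in a feasibility study too. Section 3.3.10 wants preliminary effect sizes to plan the full trial, section 3.3.14 plans between-group tests and section 3.3.16 an incremental cost-effectiveness analysis. All of these compare the two arms. Section 2.1 intends to move straight on to a full trial, so the allocation procedure tried here is likely to be carried forward.

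**Working it through.** The protocol gives no figure for school balance, so there is none to reproduce. The check has four parts.

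**1. Order of steps.** Section 3.3.3 refers to groups already generated. Section 3.3.4 randomises schools directly into the two arms and describes no stage at which unlabelled groups are reviewed before arms are attached. Section 3.3.11 masks only the analysts. Nothing read gives a criterion for equivalence, masks the local group to arm, says that the allocation stands, or says that it may be altered.

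**2. Whether stratification can secure balance.** Inputs: 4 factors and 10 + 4 = 14 schools (section 3.3.3). The fewest levels a factor can have is two.

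- Cells: 2^4 = 16.
- Schools per cell: 14/16 = 0.875 on average.

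A cell needs at least two schools before stratification can balance anything within it. Below an average of one, many cells hold one school or none, and full stratification behaves much like simple allocation.

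**3. How often a sound draw would look unequal.** Assumptions of this review: 7 v 7 schools, four independent standardised school characteristics, and no effective stratification.

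- Standard error of a standardised difference: sqrt(1/7 + 1/7) = sqrt(2/7) = 0.535.
- For one factor and limit t: p = 2 × [1 − Φ(t/0.535)].
- For at least one of four: 1 − (1 − p)^4.

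| Limit t (SD) | One factor | At least one of four |
|---|---|---|
| 0.25 | 64% | 98% |
| 0.5 | 35% | 82% |
| 0.8 | 13% | 44% |

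Stratification that works, or factors that are positively correlated, would lower the last column. The limits themselves are illustrative; the protocol sets none.

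**4. Whether limits set beforehand leave enough choice.** With exactly 10 primary schools split 5:5 and 4 secondary schools split 2:2, the possible splits number C(10,5) × C(4,2) = 252 × 6 = 1,512. Under the assumptions of step 3, the expected number within the limit on all four factors is:

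- 0.8 SD: 1,512 × (1 − 0.439) = about 848.
- 0.5 SD: 1,512 × (1 − 0.821) = about 271.
- 0.25 SD: 1,512 × (1 − 0.983) = about 26.

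The real counts depend on the schools recruited, but moderate limits should leave a genuinely random choice, and very tight ones might not.

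**The case against.** The strongest reply is that the protocol gives nobody power to alter the allocation. The only stated consequence of a concern is that the matching is considered as feasibility work, which reads naturally as learning for the full trial. On that reading a review after the draw has a legitimate use: it tests whether the chosen factors give credible groups. This stands. A reader might infer that the schools will be swapped or redrawn, but the text does not say so.

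Three other tempting readings also fail.

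- **That interested local parties can overturn the draw.** The membership and stake of the strategy group are not described. Section 6.7 puts an independent chair and at least two other independent members on the committee that hears concerns, beside the investigators.
- **That concealment is undone.** Section 3.3.4 places consent before randomisation, so a group that sees the allocation later cannot affect which children were enrolled.
- **That the group certainly sees the arms.** Section 3.3.4 makes this likely, because schools are randomised straight into arms, but it is not stated.

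It is also fair to say that the imbalance percentages ignore the planned stratification and do not measure the chance of a redraw. The word used for the process, matching, may mean that a looser scheme such as pairing is intended, which would balance better than full cross-classification. Finally, the primary outcomes are utility and acceptability, and the study is not powered for differences between arms.

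These points limit the concern. They do not answer the question of method: the planned check comes when it cannot safely improve balance, although the same local advice could be used earlier.

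**Conclusion.** The point holds as a choice of method that can be bettered cheaply. Four-factor stratification of about 14 schools has at least 16 cells and cannot secure balance if applied in full. The check that follows has no criterion, no masking and no finality rule, and it can improve balance only by altering the allocation, which would compromise the randomisation. The protocol does not say that this will happen, and the harm to the comparison would arise only if it did.

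The figures of 35% for one factor and 82% for any of four above 0.5 SD, and 44% for any of four above 0.8 SD, are illustrative upper figures. They assume 7 v 7 schools, independent factors and no effective stratification. They show that an informal check could readily find something to query after a perfectly sound draw. They are not an estimate of how often the allocation would be changed.

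**What to change.** In section 3.3.3, move the strategy group's input ahead of the draw and use constrained randomisation:

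1. Once schools are recruited and families have consented, and before any draw, ask the group which school characteristics matter and how large a difference between arms is acceptable on each.
2. Have the statistician list every split of the recruited schools that meets those limits (from up to 1,512 with exactly 10 primary schools split 5:5 and 4 secondary schools split 2:2), confirm that enough remain, and draw one at random.
3. State that this allocation is final, and that later comments on equivalence are recorded only as feasibility findings and reported to the steering committee as such.

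This keeps the local group's involvement and still yields the learning about matching that the authors want. The cost is protocol wording, an earlier consultation and a short script. The limits must leave enough acceptable splits for the draw to remain properly random, and the list must be redone if the number of schools changes, which section 3.3.3 allows for.

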3.3.4 Randomization

We will adopt a cluster randomization approach. This is to minimize the likelihood of participants in the different intervention groups being affected by changes in teacher or school behaviour. It also recognizes that social story expertise within a school is likely to be enhanced by sharing of skills and networking of ideas, and this design therefore more accurately reflects what would happen if social stories were used within a school in practice. We will use the qualitative interviewing within the feasibility design to explore this further, as described below.

To reduce detection bias we will first recruit the mainstream schools to be involved in the study. Then subsequently we will consent children and their families within these selected schools for involvement in the study. Only then will we randomize the schools into schools where the intervention takes place and those where it does not but where we are monitoring outcomes in the same way as in the intervention school. Participants will be randomised at whole school level, thus all children with ASD within any given school will be randomised to the same arm of the trial. This will minimize contamination as the likelihood of participants in the different intervention groups being affected by changes in teacher or school behaviour will be reduced. In order to limit detection bias, participants will be receive the Social Story intervention. The control school children will receive an equivalent amount of time reading a story of similar length and linguistic complexity a range of which will be chosen by the expert panel as an attention control. In both schools children will receive all other treatment or support as usual and we will monitor carefully what this is.

3.3.5 Trial Intervention

Schools will be randomised to one of two arms; the intervention group and the control group. Prior to the intervention teachers and parents of children in the intervention group will undertake training on Social Stories. We will run Social Stories training workshops informed by the earlier parts of the study. The Social Stories will be delivered in a way that is informed by the pre clinical theory and phase 1 of this study using the most promising mode of delivery. This will include who designs the Social Story with parent and child, how this is achieved, and how and when the Social Story is delivered with the child. For example this could include a teacher, support assistant, special educational needs coordinator and /or a parent and they will receive support as part of the study from the clinical researchers. The precise from of this support will be designed using findings from the pre clinical theory and phase 1 of this study.

We will check the construction of the Social Stories paying particular attention to construction guidelines as laid down by the original Social Stories model. We will also explore any other parameters, including construction, content and delivery that have been found to be related to outcome as part of the systematic review and user and expert panels. As part of this, for example, we will measure goals of the intervention, intervention agents, intervention setting, timings of the intervention, length of the intervention and number of stories per child. We will also assess characteristics such as the number and distribution of pictures and photographs, and the length and complexity of sentences, types of behaviours described and any allied interventions or support.

Whatever the precise methodology we will keep a record of all the design interactions and precise number, timings and locations of delivery. We will also record attrition, non

compliance and any distress. We will have a clear methodology of how to deal with any difficulties including child distress.

3.3.6 Control Group

Children in the control schools group will receive an attention control and treatment as usual. At the end of the study, a second free workshop will be offered to the parents of children participating in the control group on the use of Social Stories. All participants in our study will continue to be able to access care and treatment as usual throughout the trial regardless of which arm of the study they are randomised to. To clarify, no participant in either the intervention or control arm will be denied NHS treatment by virtue of participating in the trial.

3.3.7 Withdrawal

Withdrawal can occur at any point during the study at the request of the participant. If a participant indicates they wish to withdraw from the study, withdrawal will be clarified as to whether the withdrawal is from the intervention, from follow-up or all aspects of the study. Where withdrawal is only from the intervention then follow-up data will continue to be collected. Data will be retained for all participants up to the date of withdrawal, unless they specifically request for their details to be removed.

3.3.8 Duration of intervention period

The intervention for participants will be delivered over 4-6 months.

3.3.9 Inclusion and Exclusion Criteria

In the feasibility RCT stage of the study, children will only be recruited between the ages of 4-15 years, if they have a definite diagnosis of an ASD and have behavioural problems in school (as reported by parents and teachers). We will prescreen children for challenging behaviour, using clinical interviews and measures informed by the systematic review, which may include the Strengths and Difficulties Questionnaire and the Developmental Behaviour Checklist We have deliberately kept the age range broad in order to explore the acceptability of this intervention across age ranges and different settings (e.g. primary and secondary schools) and inform a fully powered trial.

This is a pragmatic trial which recognises the frequency and complexity of co-morbidities in children with autism spectrum disorders (ASD). We will therefore not exclude on the basis of comorbidity since the intervention would eventually be offered to this group if adopted more widely in the NHS. This will ensure that the research remains relevant to everyday clinical practice. This means for example that we will include children and young people with a learning disability, epilepsy, attentional problems, neurological disorders or syndromes (e.g. CHARGE syndrome, Fragile X syndrome etc). We will exclude any child from the study if they have used a Social Story within the last six months. We will exclude children and young people if they are likely to be moving school during the trial period, or if they develop behaviour or illness that warrants admission to a psychiatric unit (e.g. psychosis, serious self harm). These exclusion criteria were informed by discussions with parents who had previously used Social Stories in a focus group prior to submitting the full application. Children will only be randomised into the trial if they exhibit challenging behaviours using the validated cut offs from the Strengths and Difficulties Questionnaire or the Developmental Behaviour Checklist

3.3.10 Proposed sample size

We will use the information gathered in the pre-clinical theory stage of the study to determine sample sizes needed for the feasibility study / phase 2 of the study. The sample

size will be determined in order to be adequate to estimate the critical parameters for a full RCT. We will be estimating recruitment rate. With 50 participants in total we will be able to estimate the recruitment rate to within 10% based on 85% recruitment, using a 95% confidence interval (Dixon & Massey, 1983). We will demonstrate recruitment and follow up rates, with preliminary estimates of effect size to inform sample size calculations in a fully powered RCT.

3.3.11 Blinding

Blinding of the participants will not be feasible, nor is blinding of all members of the study team who are actively involved in the administration of the study. However, members of the study team responsible for the statistical analysis will be kept blind to group allocation.

3.3.12 Follow-up

Follow-up will be for a minimum of six months post-randomisation. Where a participant has been lost to follow-up their data will be included in the main analysis up to where they have been lost to follow-up. Where a participant is lost to follow-up, efforts will be made to contact the participant.

3.3.13 Qualitative Study

There has been little previous qualitative work exploring issues of effectiveness and acceptability of Social Stories amongst this population. An in depth appreciation of these issues will be essential for any future implementation of the manualised intervention if it proves to be clinically and cost effective. This process evaluation we will examine using semi-structured interviews, which behaviours are most problematic to children, their families and teaching staff, expectations of the technique and which of the treatment outcomes are of greatest importance to children, their families and teachers. In addition, data will be collected on the pilot trial process itself. We will ask questions relating to the acceptability of the treatment, the randomisation procedure and the methods of data collection. We will also explore qualitatively the experiences of the teachers in the context of the cluster randomisation design. We will be particularly interested in comparing those schools where several children have used the intervention compared to schools where smaller numbers of children are involved. We are interested in the systemic and individual effects. All interviews will be conducted using a topic guide to ensure consistency across participants, however, the format will be flexible in order to allow participants to generate naturalistic data on what they constitute as important and/or successful in terms of treatment outcomes.

It is anticipated a sample of 15 children and an associated family member (10 from the intervention arm and 5 from the usual care arm) would provide sufficient data to answer these questions. Trial participants will be purposively sampled on characteristics such as age, gender, extent of behavioural problems. All participants would be interviewed after the writing of the Social Story face-to-face at a location convenient for the participants with the family members; this would enhance rapport and facilitate data collection.

In addition, a sample of 5 professionals and 5 parents/carers delivering the manualised intervention will be interviewed. The interview will be semi-structured, asking them to record: their experiences associated with delivering the intervention, in particular facilitators and barriers relating to its delivery within existing service models; their perceptions of whether the intervention does or doesn't work well, including their understanding of why; and any experiences they have with users receiving the intervention which highlight where it works well and less well, including perceptions of reasons for discontinuation with the intervention by any participant.

